## **Background**

Patients with Alzheimer's disease have an increased prevalence of epileptic seizures between 1.5 and 64% (1-6). The large discrepancy between studies is partly due to differences in methods, including whether electroencephalography (EEG) has been used (1, 3, 4). EEG records the electrical activity of the brain including whether there is evidence of seizure activity (so-called paroxysmal activity). In patients with AD, EEG is helpful since the patients may have difficulty reporting seizures, symptoms of seizures can be difficult to distinguish from the symptoms of AD and a high incidence of subclinical epileptic activity (6). Conventionally, with regards to EEG, only short EEG recordings are performed (<30 min), which may not be sensitive enough due to the short recording time. With prolonged EEG recordings (6), so-called long-term monitoring for up to 24 hours, epileptic activity has been found in up to 42.2% of patients, which is higher than for short recordings. However, this method may be inconvenient for the patient as it requires hospitalization. Therefore, in the current study we will use a newly developed type of EEG device that can be placed in the ear (ear-EEG). This technique makes it possible to record EEG while the patient is in their own home over several days without significant inconvenience for the patient. The method has several advantages. First, it will be possible to do longer recordings than before, potentially over several days, and thus gain better knowledge of occurrence and frequency of epileptic activity. Second, it will be significantly less invasive for the patients than long-term monitoring during hospitalization. This equipment has not previously been used in patients with dementia but has been used in patients with epilepsy with good detection rate of epileptic activity (7). The study that investigated patients with Alzheimer's disease has also shown that 10.5% of healthy control subjects have subclinical epileptic activity [6]. Furthermore, it is known that there is an increased risk that healthy elderly will have paroxysmic activity measured by EEG. Therefore, it is also necessary to examine healthy control subjects with

ear EEG to investigate whether the incidence of subclinical epileptic activity in patients with Alzheimer's disease and Lewy body dementia is increased compared to healthy control subjects.

Furthermore, studies have found a possible link between epileptic seizures the evolution of Alzheimer's pathology (1, 8). Amyloid is believed to be involved in the processes leading to Alzheimer's disease, and transgenic mice that accumulate amyloid in the brain have epileptic activity in the hippocampus with no evidence of epileptic seizures (9). In addition, a study has shown that epileptic activity leads to decreased oxygen in the brain, leading to further deposition of amyloid. One randomized clinical trial has shown that patients with "mild cognitive impairment", which are patients who are more likely to progress to Alzheimer's disease, showed improvement in cognitive functions after 2 weeks of treatment with Levetiracetam, which is a drug used to treat epilepsy (10). Other studies have shown an increased regional blood flow (rCBF) (11, 12) in the hippocampus in patients with Alzheimer's disease, but the studies have been done on smaller groups of patients, and therefore, validation is lacking in larger cohorts of patients. In addition, the reason for the increased blood flow has not been clarified, but it could be due epileptic activity.

Patients with dementia may experience fluctuations in their cognitive functions (13), which is especially pronounced in patients with Lewy body dementia compared to patients with Alzheimer's dementia (14, 15). There are no systematic assessments of prevalence of seizures in patients with Lewy body dementia. The reported fluctuations in cognitive function could possibly be caused by epileptic seizures. We will therefore investigate whether there is epileptic activity in patients with Lewy body dementia.

## **Aim**

The overall aim of the study is to investigate whether patients with Alzheimer's disease and patients with Lewy body dementia have a higher incidence of subclinical epilepsy as compared with healthy elderly controls and whether subclinical epilepsy is correlated with blood flow in the brain as measured with MRI.

Objective 1: Investigate whether it is possible to use ear EEG for long-term monitoring of patients with Alzheimer's disease (feasibility and compliance)

Hypothesis: Ear-EEG monitoring is possible in patients with Alzheimer's disease.

Objective 2: Investigate the incidence of paroxysmal activity in patients with Alzheimer's disease and Lewy Body dementia as measured by ear EEG as compared to healthy elderly controls

The study is considered exploratory as recordings with ear EEG and also long-term EEG recordings have never carried out in this patient group before.

Objective 3: Investigate the regional blood flow (rCBF) measured by MRI in the hippocampus in patients with Alzheimer's disease.

Hypothesis: Patients with Alzheimer's disease will have an increased rCBF in the hippocampus compared to healthy controls.

Objective 4: Investigate the correlation between increased blood flow in the hippocampus and paroxysmal activity measured by the ear EEG.

Hypothesis: Increased rCBF in the hippocampus in patients with Alzheimer's disease is associated with paroxysmal activity measured by ear EEG.

## **Study Design**

The project consists of two sub-studies:

1) Feasibility study (Aim 1)

2) The main study (Aim 2-4)

Both sub-studies are longitudinal studies with 3 periods of 2 days of ear-EEG recordings in the patients' homes over 6 months. The healthy controls will undergo ear-EEG recording once. All participants must have had an MRI of the brain at the beginning of the study.

### **Feasibility study**

The first part of the project is the feasibility study in which we will recruit 10 patients with Alzheimer's disease. First visit is a screening visit where patients give informed consent (patients have also been informed on a prior visit) after which in- and exclusion criteria will be assessed. Subsequently, patients will undergo MRI of the brain on a subsequent visit. At the second visit, a conventional EEG (30 mins) at the same time as ear EEG recording will be carried out. At this visit patients will also be examined by a physician, including physical and neurological examination as well as cognitive tests, questionnaires for caregivers relating to activities of daily living and

neuropsychiatric symptoms. Patients will also undergo a blood test, and the blood test will be stored in Danish Dementia Biobank.

Afterwards, both the patient and the caregiver will receive information about epilepsy and how to detect it including instruction on how to use an epilepsy diary. In addition, they will receive training in how to use the ear-EEG, which patients have to wear for 2 days, while the caregiver is asked to take note on any symptoms of epileptic seizures they may observe.

A priori criteria for whether ear-EEG recordings are suitable in patients with AD (feasibility study) are:

> 80% of the pilot study participants can wear the ear-EEG at least 24 hours in 2 days

> 50% of the participants have recorded at least 5 hours of sleep with the ear-EEG.

### **The main study**

In the main study, we will include an additional 40 patients with Alzheimer's disease and 50 healthy control subjects as well as 20 patients with Lewy body dementia. The patients with Alzheimer's disease and Lewy body dementia will undergo the same program as for the pilot project but the total time of ear-EEG recording may be extended to up to five days.

The healthy subjects will first be examined by a physician including cognitive tests and a questionnaire on everyday activity of daily living from any relatives will be performed. On

subsequent visits, participants will undergo an MRI scan as well as a conventional EEG examination and wear the ear-EEG device for a total of 48 hours. The inclusion of healthy subjects is done in order to compare ear-EEG, conventional EEG and MRI scans in patients with AD and DLB with healthy elderly persons.

### **Statistical analysis plan**

The study is considered exploratory since recordings with ear EEG have never been performed and only one other study has looked at long-term EEG recordings.

For the feasibility study, we plan to review the EEGs together with the feedback we receive from the participants to investigate whether they were able to wear the ear-EEG at least 24 hours in 2 days, and that over 50% were able to record at least 5 hours of sleep.

If we continue with the main study, we will investigate how frequent we observed paroxysmal activity as measured on the ear-EEG in patients with Alzheimer's disease and Lewy body dementia as compared to healthy elderly controls. Furthermore, we will compare the frequency of paroxysmal activity and CBF in the hippocampus as measured with ASL-MRI.

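### Patients are to be recorded 2.5 to 3 times as long as controls, but the SAP gives its comparison of paroxysmal activity no unit and no allowance for recording time

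*Combined protocol and SAP*

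**What the plan says.** **Recording time.** Study Design gives patients in both sub-studies "3 periods of 2 days of ear-EEG recordings in the patients' homes over 6 months". It then says "The healthy controls will undergo ear-EEG recording once". The main study section has controls "wear the ear-EEG device for a total of 48 hours", and says of the AD and Lewy body patients that "the total time of ear-EEG recording may be extended to up to five days".

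**Outcome.** Objective 2 (Aim) reads "Investigate the incidence of paroxysmal activity in patients with Alzheimer's disease and Lewy Body dementia as measured by ear EEG", compared with healthy elderly controls. The Statistical analysis plan turns this into "we will investigate how frequent we observed paroxysmal activity as measured on the ear-EEG in patients with Alzheimer's disease and Lewy body dementia". For the MRI question it adds that "we will compare the frequency of paroxysmal activity and CBF in the hippocampus as measured with ASL-MRI". The Background hopes to "gain better knowledge of occurrence and frequency of epileptic activity", which treats the two as different things, and it reports earlier findings as shares of persons (up to 42.2% of patients, 10.5% of healthy controls).

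No section gives a unit, a time base, a common recording window, or a rule for combining a patient's repeated periods.

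**The concern.** The groups differ by design in how long activity can be observed. The Background itself accepts that recording time matters: it argues that short EEGs may miss activity and that longer monitoring finds it in more patients. If one group is recorded for longer and the measure ignores time, that group will show more activity even when the underlying rate is the same.

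Objective 2 carries the overall aim of the study, namely whether patients have a higher incidence than controls. If the measure is a count or an any-activity share, part or all of a patient excess could come from the schedule, and it could not be read as an effect of disease. Leaving the measure open also allows it to be chosen after the data are seen.

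**Working it through.** The documents give no test, alpha, power or sample size calculation, so there is no figure of the plan's own to reproduce.

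**Inputs from the documents**
- Patients: 3 × 2 days = 144 h (Study Design), or 5 days = 120 h if the main study's figure is a total.
- Controls: 48 h, once.
- Group sizes: 40 AD (50 if the 10 feasibility patients are pooled, which the plan does not state), 20 Lewy body dementia, 50 controls.
- 10.5% of healthy controls with subclinical activity (Background, from a cited study).

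**Assumptions made here:** 10.5% applies to 48 h of ear-EEG; hourly rates are equal in all groups; two-sided Fisher test at 5%. The within-person correlation (ICC) between 48-hour blocks is unknown and is varied.

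**1. Exposure ratio**
- 144/48 = 3.0
- 120/48 = 2.5
- If five days is meant per period: 3 × 120 = 360 h, and 360/48 = 7.5

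The two sections do not fit together: three periods of two days already make six days, which cannot be extended to a total of five.

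**2. Raw count.** The expected count is rate × hours. At equal rates the patient-to-control ratio is the exposure ratio, 2.5 to 3.

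**3. Any activity, yes/no.** With m = patient hours/48:
- ICC 0: share = 1 − (1 − 0.105)^m. For m = 3, 1 − 0.895³ = 0.283. For m = 2.5, 1 − 0.895^2.5 = 0.242.
- ICC ρ > 0: beta-binomial with a = 0.105(1 − ρ)/ρ and b = 0.895(1 − ρ)/ρ; share = 1 − B(a, b + m)/B(a, b). For ρ = 0.7 and m = 3, a = 0.045 and b = 0.3836. The share is 1 − 0.895 × (1.3836/1.4286) × (2.3836/2.4286) = 0.149.

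The chance of a significant Fisher test was then found by exact enumeration over both groups, with controls at 10.5%:

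| Patient hours | ICC | Patient share | 50 v 50 | 40 v 50 | 20 v 50 |
|---|---|---|---|---|---|
| 48 (equal time) | any | 10.5% | 1.9% | 3.1% | 2.0% |
| 120 | 0 | 24.2% | 34.4% | 34.1% | 26.6% |
| 120 | 0.3 | 19.6% | 16.1% | 17.4% | 14.6% |
| 120 | 0.7 | 14.2% | 4.2% | 5.6% | 5.3% |
| 144 | 0 | 28.3% | 53.4% | 51.4% | 39.2% |
| 144 | 0.3 | 21.8% | 24.0% | 24.6% | 19.9% |
| 144 | 0.7 | 14.9% | 5.1% | 6.6% | 6.2% |
| 72 | 0 | 15.3% | 5.8% | 7.3% | 6.8% |

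The last row takes patients at the feasibility minimum of 24 h in each 2-day period (3 × 24 = 72 h) and controls at the full 48 h.

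The base rate matters too. At 144 h, 50 v 50 and ICC 0, false positives are 21% if 5% of controls are positive per 48 h, and 82% if 20% are.

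**4. Rate per recorded hour.** If λ is the common hourly rate, patients give 144λ/144 and controls 48λ/48. Both equal λ and the rate ratio is 1, whatever the exposure ratio.

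**5. CBF analysis.** Objective 4 concerns an association within AD patients. A simulation with no true association took 50 patients, 48 to 144 h unrelated to CBF, raw counts and a Spearman test. It rejected in 5.2% of 4,000 runs, which is close to nominal.

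**The case against.** The study is declared exploratory, and the words used in the SAP (frequent, frequency) may already mean a rate over time, which would have no bias of this kind. The size of the problem on the yes/no reading depends on an ICC that nobody knows: at 0.7 the excess false positives nearly vanish. Poor wear in patients would shrink the imbalance as well, as the 72 h row shows. A negative binomial model with an offset is also only one way to deal with exposure; an equal-time window would do it too.

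Much of this stands. The documents do not settle the measure, so bias is not certain, and no single model needs to be prescribed. But the exploratory label explains the lack of a power calculation, not an undefined outcome. Objective 2's word (incidence) and the percentages of persons in the Background keep the exposed readings open. Unknown wear is a reason to use hours actually recorded.

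A reader might infer two stronger things. One is that the CBF correlation is biased in the same way. The documents do not support that: Objective 4 is framed within AD patients, where unequal hours mainly add noise. They bias the result only if recorded hours are related to CBF, or if controls are pooled with patients. The other is that the feasibility wear criterion already supplies the denominator. It covers wear in the pilot participants, judged from the EEGs together with their feedback. It does not give valid hours for every participant.

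**Conclusion.** The point holds, conditionally on the measure. Planned patient time is 2.5 to 3 times control time (7.5 if five days is per period), and the SAP neither fixes a unit nor allows for this. A raw count would be inflated by that ratio. An any-activity share would rise from 10.5% to between 14% and 28% with no true difference. False positives for 50 v 50 would be 34% to 53% at ICC 0 and 4% to 5% at ICC 0.7. If actual wear were 72 h v 48 h at ICC 0, they would be 6% to 7% across the group sizes. These figures rest on the assumed base rate, test, alpha and ICC, so they illustrate the risk and do not forecast it. It would be too strong to infer that any patient excess will be an artefact: a rate per recorded hour has no such bias, and the plan does not exclude that reading. This should be fixed before the analysis.

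**What to change.** In the SAP:

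1. State that the Objective 2 comparisons (AD v controls, Lewy body dementia v controls) use paroxysmal events per valid recorded hour, with the participant as the unit. An example is a count model with log(valid hours) as offset, giving a rate ratio and 95% CI.
2. Define the countable event and a valid hour. The rate cannot be computed without both.
3. As a sensitivity analysis, or as the fallback if a group has no events, compare any activity (yes/no) over an equal number of valid hours per participant from the first recording period.
4. Use the same hourly rate in the CBF analysis, and report valid hours by group.
5. Reconcile Study Design and The main study on total recording time.

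**Cost.** No extra recordings are needed. The work is SAP wording and deriving valid hours from the recordings of all participants, not only the pilot. The offset assumes a constant rate over recorded hours, and precision will be limited when events are few.

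The yes/no analysis gives up the later patient recordings. If 42.2% v 10.5% held over the common window, its exact Fisher power would be 95%, 93% and 79% for 50, 40 and 20 v 50. If those shares needed 48 h and only 24 valid hours were common to everyone (24.0% v 5.4% at a constant rate), it would be 68%, 67% and 52%. The Background ties the 42.2% to monitoring of up to 24 h, so which case is nearer is not known.

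### The SAP compares how often paroxysmal activity is seen on ear-EEG without an hours denominator, although patients are scheduled for three times the controls' recording time

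*Combined protocol and SAP*

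**What the plan says.** **Outcome.** For Objective 2, the Statistical analysis plan states that "we will investigate how frequent we observed paroxysmal activity as measured on the ear-EEG in patients" with AD and DLB, against healthy elderly controls. It then relates the frequency of this activity to hippocampal blood flow (Objective 4). It does not say whether frequency means the proportion of people with any activity, a number of events, or events per unit of time. It gives no rule for what counts as interpretable recording.

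**Recording time.** Study Design gives patients "3 periods of 2 days of ear-EEG recordings in the patients' homes over 6 months" and has controls recorded once. The main study says controls have a "conventional EEG examination and wear the ear-EEG device for a total of 48 hours". Main-study patients "will undergo the same program as for the pilot project", with total recording time possibly extended to as much as five days.

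**Signal checks.** The Feasibility study section introduces its two thresholds with "A priori criteria for whether ear-EEG recordings are suitable in patients with AD (feasibility study) are". One concerns wear (at least 24 hours in 2 days) and the other recorded sleep (at least 5 hours). For the pilot, the SAP says "we plan to review the EEGs together with the feedback we receive from the participants", which it ties to those thresholds. Background says the device has shown good detection in epilepsy but has not been used in dementia.

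**Paired recording.** At the pilot's second visit, "a conventional EEG (30 mins) at the same time as ear EEG recording will be carried out", and main-study patients inherit that program. The main study adds that "The inclusion of healthy subjects is done in order to compare ear-EEG, conventional EEG and MRI scans" between patients and healthy persons. The SAP does not mention conventional EEG.

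**The concern.** The chance of seeing at least one paroxysmal event rises with the hours that can be read. A between-group comparison therefore needs either equal exposure or an hours denominator. The plan has neither: the schedules differ by a factor of three and no denominator is named.

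The figures that Background uses as context (up to 42.2% of AD patients, 10.5% of healthy controls) are proportions of people. A reader would naturally expect this study to report the same measure. On that measure, the schedule alone can make patients look worse than controls.

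A second influence runs the other way. If dementia patients at home produce less readable signal per worn hour, their activity is under-counted. The plan reports nothing by group that would reveal this. The feasibility thresholds suit Objective 1, but they apply to 10 AD pilot patients and do not reach the DLB patients, the controls or the main-study outcome.

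Objective 4 is affected differently. Within AD patients the nominal schedule is the same, but hours actually worn and readable, and any extension, will vary between patients. An unadjusted frequency would carry that variation into its relation with blood flow.

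**Working it through.** The plan states no power, test or target difference, so it has no figure of its own to reproduce. What follows illustrates the size of the exposure effect.

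**Inputs from the document**
- Patients: 3 periods × 2 days × 24 h = 144 h (Study Design).
- Controls: 48 h once (Study Design; The main study).
- Exposure ratio: 144 / 48 = 3.
- AD: 10 pilot + 40 main-study = 50. Controls: 50. DLB: 20.
- Healthy-control proportion: 10.5% (Background).

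**Assumptions**
- 10.5% is the chance of any activity in 48 h, in both groups, so there is no true difference. Background does not give the recording length behind this figure.
- Events occur at a constant rate, the same in every person.
- All scheduled hours are worn and readable.
- AD pilot and main-study patients are pooled.
- A two-sided Fisher test at 0.05 is used; the SAP names no test.

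**Step 1: proportion expected to show any activity.** With k times the reference exposure, P = 1 − (1 − p)^k.
- Controls, k = 1: 10.5%, or 50 × 0.105 = 5.3 people.
- Patients, k = 3: 1 − 0.895³ = 1 − 0.717 = 28.3%, or 50 × 0.283 = 14.2 people.

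**Step 2: how often the test calls this a difference.** Sum the product of the two binomial probabilities over all pairs of counts with Fisher p ≤ 0.05.
- 50 vs 50, 28.3% vs 10.5%: 53%.
- 50 vs 50, 10.5% vs 10.5% (equal exposure): 1.9%.
- Unpooled AD, 40 vs 50, 28.3% vs 10.5%: 51%.
- DLB, 20 vs 50, 28.3% vs 10.5%: 39%.

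**Step 3: dependence on the equal-rate assumption.** Suppose only a fraction s of people can show activity, with 10.5% overall still detected in 48 h. Then P over 144 h = s × [1 − (1 − 0.105/s)³].
- s = 1: 28.3%; Fisher 53%.
- s = 0.5: 0.5 × (1 − 0.79³) = 25.3%; Fisher 40%.
- s = 0.2: 0.2 × (1 − 0.475³) = 17.9%; Fisher 11%.

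The inflation shrinks as activity concentrates in fewer people, but its direction does not change.

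**Step 4: extension.** The document does not say whether five days applies to each period or in all. Five days in all is 120 h, less than the scheduled 144 h. Five days in each of three periods is 360 h, or k = 7.5, and 1 − 0.895^7.5 = 56.5%.

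**Step 5: the opposing influence.** Interpretable hours would be equal only if the readable share of patients' hours were one third of the controls' (144 × 1/3 = 48). The document gives no readability figure for any group, so where the net effect falls between these influences cannot be estimated.

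**The case against.** **Frequency may already mean a rate.** The SAP speaks of how frequent the activity is, not of a raw count. If events per hour of recording were meant, the schedule would not bias the comparison. That stands as a possible reading, but the text does not say it, and it would still leave interpretable hours undefined.

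**The study is exploratory.** This excuses the lack of a power calculation or formal test. It does not excuse an outcome without a denominator, because a descriptive table misleads in the same way.

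**The device is known to detect epileptic activity.** Background does cite good detection in epilepsy, so the open question is narrow: readability in dementia patients at home. The recorded-sleep threshold and the pilot EEG review give a partial check, in 10 AD patients only.

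**A reader might infer that poor signal will hide a true difference.** With Background's 42.2% for AD and half the controls' interpretable hours, a uniform event rate gives 1 − 0.578^0.5 = 24.0%, and Fisher power against 10.5% (50 vs 50) falls from 95% to 33%. The documents do not support this as a forecast. It needs patients to have fewer interpretable hours, when they are scheduled for three times as many. It also depends on the model: if 45% of patients are susceptible, the same halving gives 33.8% and 76%.

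**A reader might infer that activity and unreadable signal can never be told apart.** That is too strong. Readable time can be scored from recordings already planned; what is missing is the instruction to do so.

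**A reader might infer that the unanalysed paired EEG leaves home readability unproven.** Thirty minutes is about 1% of 48 h (0.5 / 48), at one visit. Analysing it would not establish home readability either.

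**Conclusion.** The point holds. The main-study comparison has no recorded or interpretable-hours denominator while scheduled recording is 144 h against 48 h. If the measure is the proportion with any activity, the schedule biases it towards more activity in patients. With identical true rates of 10.5% per 48 h, patients would show 28.3%, and about 53% of such studies would give a significant Fisher test instead of about 2%.

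Those figures rest on a constant rate shared by everyone, full wear and readability, pooled AD patients, and an assumed test. They come down to 17.9% and 11% if only a fifth of people can show activity.

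Lower readability in patients would work against this bias by an amount the documents do not allow anyone to estimate. The defect is therefore that the comparison cannot be interpreted as written, not that its error has a known net direction. It should be corrected before the main-study recordings are reviewed.

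**What to change.** Leave the two feasibility criteria as they are. Add to the Statistical analysis plan:

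1. **Definition.** Define interpretable ear-EEG before the main-study EEGs are reviewed. If pilot EEGs have already been read, label the pilot summaries post hoc.
2. **Hours.** Report worn and interpretable hours per participant (median and range) for AD, DLB and controls.
3. **Objective 2.** Compare the proportion with any paroxysmal activity over a common exposure: the patients' first 48 h period against the controls' 48 h, as n/N with exact 95% confidence intervals. Beside it, give the frequency per interpretable hour using all periods.
4. **No readable signal.** List participants with no interpretable recording as not assessable, not as negative.
5. **Objective 4.** Use the frequency per interpretable hour.
6. **Optional, descriptive only.** Tabulate the simultaneous 30-minute recordings in patients: share of ear-EEG interpretable, and activity present or absent on each method. State that this does not validate home signal. Include controls only if their two recordings were simultaneous, which the protocol does not say.

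**Cost.** No new visits or recordings. Readers mark interpretable time during a review that is already planned, over 70 × 144 + 50 × 48 = 10,080 + 2,400 = 12,480 recording hours if every scheduled hour is worn, and more if recording is extended. Per-hour frequencies are unstable in people with few interpretable hours, so they belong beside the proportions and not in place of them. The common-exposure comparison sets aside the patients' later periods, which enter only through the per-hour frequency.

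### The patient–control comparison of paroxysmal activity does not allow for longer recording in patients and does not say how age is handled

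*Combined protocol and SAP*

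**What the plan says.** The Statistical analysis plan gives the Objective 2 comparison in one sentence. The quantity to be examined is "how frequent we observed paroxysmal activity as measured on the ear-EEG", and the contrast is stated as "in patients with Alzheimer's disease and Lewy body dementia as compared to healthy elderly controls". No effect measure, test, model, covariate or observation window is named, and it is not said whether the outcome is a yes/no result per participant or a count.

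On recording time, Study Design describes both sub-studies as "longitudinal studies with 3 periods of 2 days of ear-EEG recordings" at home over six months, and then adds: "The healthy controls will undergo ear-EEG recording once". The main study section gives controls 48 hours and says that total recording in patients may be extended to at most five days. Three periods of two days already make six, so these two sections must be reconciled.

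On age, the Background states that "it is known that there is an increased risk that healthy elderly will have paroxysmic activity measured by EEG" and gives this as a reason for having controls. It also cites a study in which "10.5% of healthy control subjects have subclinical epileptic activity". Controls are described throughout as healthy elderly people. The Feasibility study section mentions a screening visit "after which in- and exclusion criteria will be assessed", but the criteria are not in the supplied text.

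**The concern.** The overall aim is to say whether patients with Alzheimer's disease (AD) or Lewy body dementia (DLB) have a higher incidence than healthy elderly controls. The groups are formed by diagnosis, so any other systematic difference between them enters the contrast.

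Recording time differs by design and always in the same direction. The chance of seeing at least one event rises with hours observed, so an ever-observed comparison favours a patient excess even if the disease has no effect. The protocol's own case for ear-EEG is that longer recording finds more activity.

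Age may also differ, in either direction. A confidence interval shows sampling error, but it shows neither of these biases.

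**Working it through.** The documents contain no sample size, power or effect calculation, so there is no figure of the plan to reproduce.

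**Inputs from the documents.** Control rate 10.5% and AD rate up to 42.2% (Background, one cited study). Controls 48 hours; patients six days (Study Design) or up to five (The main study). Group sizes 10 + 40 AD, 20 DLB and 50 controls. Pooling the 10 feasibility patients is an assumption.

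**1. Recording time, yes/no outcome.** Assume equal underlying rates in patients and controls and independent periods. Then P(any activity) = 1 − (1 − p)^(ratio of recording times).

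*If 10.5% applies to 48 hours* (control odds 0.105/0.895 = 0.117):
- Five days: 1 − 0.895^2.5 = 24.2%; odds ratio (0.242/0.758)/0.117 = 2.72.
- Six days: 1 − 0.895^3 = 28.3%; odds ratio (0.283/0.717)/0.117 = 3.37.

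*If 10.5% applies to 24 hours* (the Background cites the same study for monitoring of up to 24 hours):
- Controls at 48 hours: 1 − 0.895^2 = 19.9%.
- Five days: 1 − 0.895^5 = 42.6%; odds ratio 2.98.
- Six days: 1 − 0.895^6 = 48.6%; odds ratio 3.81.

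**2. Effect of the independence assumption.** If some people show activity repeatedly and others never, extra days add fewer new positives. Let rates vary between people as a gamma distribution with shape k and mean m per 48 hours. Then P(any) = 1 − (1 + m·t/k)^(−k), where t is recording time in units of 48 hours and m is set so that P(any) = 10.5% at t = 1.

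| k | m | Odds ratio, five days | Odds ratio, six days |
|---|---|---|---|
| 1.0 | 0.117 | 2.50 | 3.00 |
| 0.3 | 0.134 | 2.15 | 2.48 |
| 0.1 (strong clustering) | 0.203 | 1.69 | 1.85 |

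The bias shrinks with clustering but keeps its direction.

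**3. Count outcome.** If events are counted without dividing by hours, equal rates give expected count ratios of 120/48 = 2.5 or 144/48 = 3.0.

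**4. Sampling error for scale.** At 10.5% in both groups, 50 v 50, the SE of the log odds ratio is √(2/(50 × 0.105 × 0.895)) = 0.652. The 95% interval therefore spans a factor of exp(1.96 × 0.652) = 3.6 either way. For 20 v 50 the SE is 0.863 and the factor 5.4.

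**5. Age.** The documents give no age gap, age spread or slope, so all three are assumed: odds rising 3% to 8% per year, SD 5 to 9 years. A logistic model in age was averaged over each group's ages and calibrated to 10.5% in controls, with no disease effect.

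| Age gap | Odds ratio, patients older | Odds ratio, patients younger |
|---|---|---|
| 2 to 5 years | 1.06 to 1.46 | 0.68 to 0.94 |
| 10 years | 1.34 to 2.13 | 0.47 to 0.75 |

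As a hand check, slope^gap gives 1.03^2 = 1.06, 1.08^5 = 1.47 and 1.08^10 = 2.16.

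**6. Cost of age adjustment.** In simulations with Firth logistic regression (group and age only, SD 7, true odds ratio 2), the SE of the log odds ratio rose 1% to 4% at a 2-year gap and 5% to 9% at a 5-year gap. At a 10-year gap, ordinary logistic regression with no disease effect and an age odds ratio of 2.0 per decade (50 v 50) raised the median SE from 0.58 to 0.73, about 26%. It also moved the median odds ratio from 1.94 to 0.98.

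**The case against.** The strongest reply is that the study calls itself exploratory and the SAP is a short outline. No method is named, so no wrong method has been chosen. That is fair. A reader might infer that the plan commits itself to a crude comparison only, but the text does not say so. What stands is that nothing in it sets a common observation window, and the schedule makes the windows unequal.

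On age, the objection largely stands. Eligibility criteria are not in the supplied text, so age limits or matching may already exist. Choosing elderly controls reduces any gap. The Background does not say that risk keeps rising with age among older people. A reader might infer that age bias is known to be present, or that it is modest. Neither is supported, since the gap and slope are both unknown and the odds ratio under no effect depends on them.

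Three further readings go too far:
- That the whole contrast in the cited study, 42.2% v 10.5% (odds ratio 6.2), could be an artefact of recording time or age. None of the five-day, six-day or age scenarios above reaches 6.2.
- That age should also be a covariate for the blood-flow hypothesis, "Patients with Alzheimer's disease will have an increased rCBF in the hippocampus compared to healthy controls". The documents do not link age to hippocampal blood flow.
- That too few events are expected to allow any covariate beyond age. Expected events depend on whether the 10.5% refers to 24 or 48 hours, which is not stated.

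**Conclusion.** The concern holds, mainly for recording time. Unequal recording is written into the design, and it biases any ever-observed comparison, or any raw count, towards a patient excess. With independent periods and equal underlying rates the spurious odds ratio is 2.7 to 3.4, or about 3.0 to 3.8 if the 10.5% is a 24-hour figure. It falls to about 1.7 to 1.8 under strong clustering within people. For a study of this size that is large enough to be taken for a disease effect. It does not arise if the analysts already intend equal windows or a rate per hour, but the SAP does not say so.

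Age is secondary. The supplied text does not state how it is handled, and the possible bias ranges from negligible to an odds ratio of about 2, depending on assumed inputs.

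Both matters are cheap improvements to an exploratory plan. They are not grounds to doubt the study as a whole.

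**What to change.** **Recording time.** State in the SAP that the Objective 2 group comparison uses each participant's first 48-hour recording period, with hours actually recorded reported by group, because wear time within 48 hours may differ. If the outcome is a count, compare rates per recorded hour instead. Say which type of outcome is meant. Keep later patient recordings for description within patients. Reconcile the recording time in Study Design with that in The main study.

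**Age.** State how age is handled and report age by group. Beside the unadjusted result, give an exploratory age-adjusted estimate with 95% CI for AD v controls and for DLB v controls. For a yes/no outcome, use a small-sample method such as Firth logistic regression. If matching was used, say so and account for the matching factors.

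**Cost.** SAP wording only, assuming that age and recorded hours are captured. The 48-hour window leaves later patient recordings out of the group contrast. Age adjustment widens intervals slightly (SE up about 1% to 9% for gaps up to 5 years), and more if the age gap proves large. The DLB estimate will be imprecise with or without it.
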